12.1.7.1. Evaluation of Treatment-emergent Elevated Liver Function Tests

The following assessments should be performed in the event one of the following laboratory results occurs after study drug administration:

- ALT > $3 \times$ ULN OR
- AST $>3 \times$ ULN OR
- Total bilirubin $>2 \times ULN$
- 1. Review of medical history and concomitant treatment or drug use.

In this study of opioid withdrawal symptoms during opioid dose tapering, the occurrence of significant hepatic injury is most likely to arise from etiologies that are extraneous to the treatment protocol. Study subjects, though voluntarily seeking reduction or cessation of chronic opioid treatment, are known to have both physiological as well as psychologic responses to large reductions in opioid dose. These responses may include maladaptive behaviors that can result in hepatotoxic outcomes; thus, initial medical history and laboratory investigation should focus on whether any of the following has occurred:

• Hepatoxic doses of acetaminophen with or without co-consumption of alcohol

Note: If the medical history confirms high dose acetaminophen use, *immediately* refer the subject to a hospital emergency room where a serum tox screen should be performed that includes acetaminophen levels. Acetaminophen toxicity can be subtle yet does respond to acute intervention.

- Hepatic injury due to acute binge alcohol consumption
- Acute hepatitis due to viral transmission from the unsterile injection of illegally obtained narcotics
- Hepatoxicity arising from the compensatory use of legal or illegal herbal supplements taken to address opioid withdrawal syndrome
- 2. Assess for symptoms and perform repeat laboratory tests within 48-72 hours.

Determine if subject is symptomatic (ie, assess for nausea, vomiting, anorexia, abdominal pain, or fatigue) and perform repeat testing (including ALT, AST, international normalized ratio, total and direct bilirubin, viral hepatitis panel, a urine drug screen, and if necessary, urine test for ethyl glucuronide) within 48-72 hours. A urine test for ethyl glucuronide is needed as part of repeat laboratory testing if alcohol use is suspected (ie, necessary if Visit 4 urine test results for ethyl glucuronide showed presence of the metabolite in the urine).

If symptoms persist OR repeat testing shows either of the following, initiate close observation follow-up plan:

- ALT and/or AST $>3 \times$ ULN for subjects with normal baseline measures OR
- ALT and/or AST of a 2-fold increase above baseline values for subjects with elevated values before study drug exposure.
- 3. Develop and implement a close observation follow-up plan (if applicable).

A close observation follow-up plan should be determined as appropriate for the subject by the Investigator in consultation with the Medical Monitor. Close observation procedures include, but are not limited to, the following:

- Repeating liver enzyme and serum bilirubin tests 2-3 times weekly. Frequency of retesting can decrease to once a week or less if abnormalities stabilize or the trial drug has been discontinued and the subject is asymptomatic.
- Obtaining a more detailed history of symptoms and prior or concurrent diseases.
- In the absence of an etiology, consider evaluating for autoimmune or alcoholic hepatitis, nonalcoholic steatohepatitis, hypoxic/ischemic hepatopathy, and biliary tract disease.
- Obtaining a history of exposure to environmental chemical agents.
- Considering gastroenterology or hepatology consultations.

All subjects meeting criteria for elevated liver function tests following study drug administration should be followed until all abnormalities return to normal or to the baseline state.

4. Discontinuation from study drug with safety follow-up through EOS period or until AE has resolved.

Subjects should be discontinued from the study drug if:

- ALT or AST $>5 \times$ ULN in 2 consecutive tests.
- ALT or AST $>3 \times$ ULN with the appearance of fatigue, nausea, vomiting, right upper quadrant pain or tenderness, fever, rash, and/or eosinophilia (>5%).

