- ¹ Phone call will take place on Day 25, to check on the subject's well-being and to assess how the subject is feeling.
- ^m Phone calls will take place on Days 32, 39, and 46, to check on the subject's well-being and to assess how the subject is feeling.
- ⁿ Reminders contacts may be done via phone, text, or other electronic message. Remind the subjects about opioid dose reductions or, at Day 17, study drug dose reductions.
- Opioid dose will be decreased 50% from baseline MED beginning with the last dose of the day on Day -1, an additional 25% of baseline MED beginning on Day 6, and a final 25% (to dose of zero) beginning on Day 13. Opioid dose reduction may not occur on a Friday or Saturday unless the clinic can accommodate

subjects on Saturday and Sunday. Subjects who experience intolerable withdrawal symptoms despite increasing their dose of study drug to the maximum tolerated dose will be allowed to pause the opioid taper once. See Table 3 for the opioid taper schedule for subjects who must pause the taper.

- ^p Detailed study drug dosing information can be found in Section 9.2.3. Study drug taper begins on Day 18.
- ^q Subject interview will be conducted via a centralized interviewer through a phone call. The interview should take place no more than 5 days after the EOS Visit.
- ^r Training includes when to call the site due to symptoms of hypertension or hypotension, or if the subject records a vital signs measurement that meets the criteria to contact the site.
- ^s Training includes recording all pharmacologic and non-pharmacologic concomitant treatments (including opioid medications), study drug dose administration, scale assessments for both pain (Average Daily and Worst Daily NRS) and opioid withdrawal scales (SOWS-Gossop, SOWS-Handelsman, and MCGI-Subject), and recording of at-home vital signs (during study drug taper and through EOS only).

	Screeni	ing ^a							Study 1	Drug	Admi	nistra	tion ^b									Safety I	Follow-ı	ap
Method	Screenin g	RC	Visit 1	PC 1	Visit 2	RC		PC 2	Visit 3	RC		PC 3	Visit 4	RC		PC 3P	Visit 4P	RC	PC 4	Visit 5	PC 5	EOS	PCs 6,7,8	30-day PC 9
Timing	Days -28 to -2	Day -1	Day 1	Day 2	Day 3	Day 5	Day 6	Day 7	Day 8	Day 12	Day 13	Day 14	Day 15	Day 18	Day 19	Day 20	Day 21	Day 23	Days 24- 27	Day 28	Days 29- 33	Day 34		Follow -up ^c
Visit window					±1 day				±1 day				±1 day				±1 day			±1 day		±1 day		
Informed consent and HIPAA authorization	Х																							
Inclusion/exclusio n	Х																							

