- ¹ Phone call will take place on Day 31, to check on the subject's well-being and to assess how the subject is feeling.
- ^m Phone calls will take place on Days 38, 45, and 52, to check on the subject's well-being and to assess how the subject is feeling.
- ⁿ Reminders contacts may be done via phone, text, or other electronic message. Remind the subjects about opioid dose reductions or, at Day 24, study drug dose reductions.
- ^o Opioid dose will be decreased 50% from baseline MED beginning with the last dose of the day on Day -1. The opioid dose will be decreased or maintained beginning on Day 6. The opioid dose will be decreased an additional 25% of baseline MED or maintained beginning on Day 13. A final 25% (to dose of zero) reduction will be made beginning on Day 19. Subjects who experience intolerable withdrawal symptoms despite increasing their dose of study drug to the maximum tolerated dose will be allowed to pause the opioid taper once. Pausing the opioid taper includes either a return to the last stable opioid dose for the remainder of the current opioid dose reduction period (eg, if a subject experiences intolerable withdrawal at the second reduction stage [25% of baseline MED], they can return to the first reduction dose [50% of baseline MED]), or remaining on the current opioid dose instead of reducing at the next scheduled reduction, resulting in an overall extended opioid taper period and study duration. In this scenario, a subject will taper to a dose of zero beginning on Day 19. Opioid dose reduction may not occur on a Friday or Saturday unless the clinic can accommodate subjects on Saturday and Sunday.
- ^p Detailed study drug dosing information can be found in Section 9.2.3. Study drug taper begins on Day 24.
- ^q Subject interview will be conducted via a centralized interviewer through a phone call. The interview should take place no more than 5 days after the EOS Visit.
- ^r Training includes when to call the site due to symptoms of hypertension or hypotension, or if the subject records a vital signs measurement that meets the criteria to contact the site.

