7.4. Duration of Subject Participation

The study duration for each subject will be up to 85 days. The Screening period is up to 28 days, the study drug administration period (including a 4-day study drug taper) is 21 to 27 days (the latter for those requiring an extended opioid taper), and a 30-day safety follow-up period.

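### The liver stopping rule relies in part on eosinophils above 5%, but no eosinophil count after the first dose is scheduled or named in the repeat tests

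*Combined protocol and SAP*

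**What the plan says.** Section 12.1.7.1 lays out steps to follow when ALT or AST exceeds 3×ULN, or total bilirubin exceeds 2×ULN, after study drug has been given.

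- **Step 2, repeat tests.** Within 48–72 hours the site is to "perform repeat testing (including ALT, AST, international normalized ratio, total and direct bilirubin, viral hepatitis panel, a urine drug screen", plus a urine alcohol marker where needed.
- **Step 2, entry to close observation.** Observation starts if symptoms persist, if the repeat ALT or AST is above 3×ULN (normal baseline), or, for raised baselines, on "ALT and/or AST of a 2-fold increase above baseline values for subjects with elevated values before study drug exposure".
- **Step 3, close observation.** The one routine blood test named is "Repeating liver enzyme and serum bilirubin tests 2-3 times weekly". The list is open-ended and the plan is agreed with the Medical Monitor. Everyone who meets the liver criteria "should be followed until all abnormalities return to normal or to the baseline state".
- **Step 4, stopping.** Study drug stops for ALT or AST above 5×ULN on two consecutive tests, or above 3×ULN "with the appearance of fatigue, nausea, vomiting, right upper quadrant pain or tenderness, fever, rash, and/or eosinophilia (>5" (percent).

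Table 10 lists eosinophils under hematology only. Tables 2 and 3 mark hematology at Screening and nowhere else; clinical chemistry is marked at Screening, Day 15 and End of Study (EOS).

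On timing, Table 2 notes "Study drug taper begins on Day 18" and Table 3 notes "Study drug taper begins on Day 24". Section 7.4 gives a dosing period that "is 21 to 27 days (the latter for those requiring an extended opioid taper").

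**The concern.** A percentage limit on a blood cell count cannot be judged at the bedside; it needs a sample. As written, the plan makes eosinophilia a reason to stop the drug but never calls for the test that would show it. For a subject at more than 3 and up to 5×ULN who feels well and has no fever or rash, eosinophilia is the only limb of the second stopping criterion left, and whether it is looked for depends on the site. With 7 sites, practice can differ.

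This touches the trial's purpose. The synopsis names hepatotoxicity among the signals the trial is meant to look for, and Section 6.4 lists monitoring for drug-induced liver injury among the tools for the primary objective.

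Reading the same steps together shows a second inconsistency. For some raised baselines, the limit that starts closer watching lies above the limit that counts towards stopping.

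**Working it through.** The plan states no figure to reproduce. The check has three parts.

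**1. Where a post-dose eosinophil count could come from**

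| Source | Eosinophil count planned after first dose |
|---|---|
| Table 2, visits on Days 3, 8, 15, 22, 28 | 0 |
| Table 3, visits on Days 3, 8, 15, 21, 28, 34 | 0 |
| Repeat panel, step 2 | none named |
| Close observation, step 3 | none named |
| Early discontinuation (Section 8.6, uses EOS tests) | none; EOS has chemistry only |

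The hematology row has one mark in each table and the chemistry row has three, so a mark lost in text extraction is unlikely.

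**2. How many dosing days are at stake**

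The only scheduled on-drug liver draw is Visit 4, Day 15 ± 1, that is Day 14–16. EOS (Day 28 or 34) follows the last dose. The last dose is Day 21 in the standard schedule (drug taper Days 18–21) and Day 27 in the pause schedule (Days 24–27). The result time of 1–2 days is an assumption. The text does not say when the 48–72 hours start, so both readings are shown.

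| | Clock from the draw | Clock from the first result |
|---|---|---|
| First result | not used | 14+1 = 15 to 16+2 = 18 |
| Redraw | 14+2 = 16 to 16+3 = 19 | 15+2 = 17 to 18+3 = 21 |
| Eosinophil result | 16+1 = 17 to 19+2 = 21 | 17+1 = 18 to 21+2 = 23 |
| Dosing days left, standard | 21−17 = 4 to 21−21 = 0 | 21−18 = 3 to 0 |
| Dosing days left, pause | 27−17 = 10 to 27−21 = 6 | 27−18 = 9 to 27−23 = 4 |

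Over both readings, 0–4 days remain in the standard schedule and 4–10 in the pause schedule. These are the days saved if the drug stops at once.

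Section 12.1.7.1 does not say whether it does. Section 8.6 tells subjects who leave the study early to taper the drug over 4 days. If that applies, the last dose is the result day + 4:

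- Standard: 21 − (17+4) = 0, so nothing is saved.
- Pause: from 27 − (17+4) = 6 down to 27 − (23+4) = 0 days saved.

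**3. The observation limit for raised baselines**

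Exclusion criterion 2 allows ALT or AST up to 3×ULN. Reading the 2-fold rule as 2 × baseline:

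- Baseline 2.5: 2 × 2.5 = 5.0×ULN, equal to the stopping limit.
- Baseline 2.8: 2 × 2.8 = 5.6×ULN.
- Baseline 3.0: 2 × 3.0 = 6.0×ULN.

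The order reverses above 5/2 = 2.5×ULN, and the affected band is at most 6.0 − 5.0 = 1.0×ULN wide.

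Example: a symptom-free subject has baseline 2.8, Day 15 value 4.6 and repeat 5.3×ULN. Only one value exceeds 5, so step 4 is not met. Since 5.3 < 5.6, observation is not triggered either. The 2–3 times weekly retest that could supply the second value above 5×ULN does not start.

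**The case against.** The best reply is that nothing prevents the test. The repeat panel is introduced as non-exhaustive, the observation list is open, and Section 12.1.7 lets the investigator order further tests at any time. An investigator who checks step 4 sees the eosinophil limit there and can act on it. The laboratory manual, which is not among the documents, may name the test. All of this shows that the count is allowed. None of it prompts the count in the protocol: step 2 spells out its panel, including when the alcohol marker is needed, yet leaves out a laboratory value on which step 4 depends.

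The second reply is that the affected group is narrow, and this stands. Fatigue, nausea and vomiting are likely during opioid withdrawal, so the symptom limbs will often apply first. The 5×ULN limb needs no eosinophil count, and Section 8.5 allows a subject to be stopped at any time.

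The third reply concerns the raised-baseline point. The example subject must still be followed to resolution, and Section 12.1.7 requires clinically significant values to be repeated. That is correct, but neither rule sets an interval. Exclusion criterion 5 and the general-health inclusion criterion may also keep out some such baselines, so cases among 60 subjects should be rare.

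**Conclusion.** The concern holds and is minor. Followed exactly as written, the plan leaves one numeric limb of a liver stopping rule without data for a subject at more than 3 and up to 5×ULN who has none of the listed symptoms or signs.

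The consequence is small in the standard schedule, where the result arrives around the drug taper, and somewhat larger in the pause schedule. The size rests on the assumed 1–2 day result time and on whether the drug is stopped outright or tapered.

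The raised-baseline inversion is real but rare. It depends on reading the 2-fold rule as 2 × baseline and should be treated as a consistency correction only.

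**What to change.** 1. In step 2 of Section 12.1.7.1, add a white-cell differential to the 48–72 hour repeat panel.
2. In the raised-baseline bullet, set the observation limit at the lower of 2 × baseline and 5×ULN. The limit becomes 5×ULN for baselines of 2.5–3.0×ULN and is unchanged below 2.5×ULN. In the example, 5.3 > 5.0, so observation would start.

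The cost is wording in two places and one extra tube, only for subjects already being redrawn. A count above 5% from an unrelated cause could stop an occasional subject; the Screening differential shows whether the finding is new. The second change adds retests only for the rare subject described. No visit, sample size or analysis changes.

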12.2. Adverse and Serious Adverse Events

AEs will be assessed by asking the subject, "How have you been feeling since I saw you last?" The study physician will review current AEs with the subject and assess any AEs unresolved from the previous visit. The type of AE, whether serious or non-serious, severity, and the relationship to study drug will be recorded by the physician in the subject's source document and eCRF after each AE assessment. The physician's clinical judgment will be used to assess the severity and relatedness of each AE.

12.2.1. Definition of Adverse Events

12.2.1.1. Adverse Event

An AE is any untoward medical occurrence in a subject participating in a clinical study. An AE includes any noxious, pathologic, or unintended change in anatomic, physiologic, or metabolic functions as indicated by physical signs, symptoms and/or laboratory changes. An unexpected AE is an AE not identified in nature, severity, or frequency in the current package insert for LUCEMYRA [USWM 2018].

Anticipated fluctuations of pre-existing conditions that do not represent a clinically significant exacerbation or worsening need not be considered AEs. Study events occurring after signing

informed consent, but prior to study drug administration, are to be documented in the subject's medical history source and eCRF.

For any pain-related AE, the subject will be questioned regarding changes since pre-study pain.

12.2.1.2. Serious Adverse Event

An SAE is defined as an AE meeting any of the criteria, in the view of either the Investigator or Sponsor, in Table 11.

Serious Adverse Event Criterion	Guidance
Results in death	Any event resulting in a fatal outcome must be fully documented and reported, including deaths occurring within 4 weeks after the treatment ends and irrespective of the causal relationship to the investigational product. The death of a subject enrolled in a study is per se not an event, but an outcome.
Is life-threatening	The term life-threatening refers to an adverse event in which the subject was at immediate risk of death at the time of the event. It does not refer to an event, which may have caused death if it were more severe.
Requires in-patient hospitalization or prolongation of existing hospitalization	The term hospitalization means that the subject was admitted to hospital or that existing hospitalization was extended as a result of an event. Hospitalization describes a period of at least 24 hours. Overnight stay for observation, stay at emergency room, or treatment on an outpatient basis do not constitute a hospitalization. However, medical judgment must always be exercised and when in doubt the case should be considered serious (ie, if case fulfills the criterion for a medically important event). Hospitalizations for administrative or social purposes do not constitute a serious adverse event. Hospital admissions and/or surgical operations planned before study inclusion are not considered adverse events, if the illness or disease existed before the subject was enrolled in the study, provided that the condition did not deteriorate during the study.
Results in persistent or significant disability/incapacity or substantial disruption of the ability to conduct normal life functions	Disability/incapacity means a substantial disruption of a person's ability to conduct normal life functions. In doubt, the decision should be left to medical judgment by the Investigator.
Is a congenital anomaly/birth defect	Congenital anomaly/birth defect observed in any offspring of the subject conceived during treatment with the investigational product.
Is an important medical event	Important medical events are events that may not be immediately life threatening or result in death or hospitalization but may jeopardize the subject or may require medical or surgical intervention to prevent one of the other outcomes listed in the definition above. Examples of important medical events include adverse events that suggest a significant hazard, contraindication or precaution, occurrence of malignancy or development of drug dependency or drug abuse. Medical and scientific judgment should be exercised in deciding whether events qualify as medically important.

Table 11:Definition of Serious Adverse Event

12.2.2. Relationship of Adverse Event to Study Drug

For each AE, the Investigator must assess the attribution of the study drug to the AE and determine whether the AE is or is not related to the study or test drug as defined below. When in doubt, the AE should be considered at least "possibly related" until further evidence becomes available to refute this assessment.

Definitely Not Related

Subject did not receive the test drug, the temporal sequence of the AE onset relative to administration of the test drug is not reasonable, or there is another obvious cause of the AE.

Possibly Related

There is evidence of exposure to the test drug, the temporal sequence of the AE onset relative to administration of the test drug is reasonable, but the AE could have been due to another equally likely cause.

Probably Related

There is evidence of exposure to the test drug, the temporal sequence of the AE onset relative to administration of the test drug is reasonable, and the AE is more likely explained by the test drug than by any other cause.

Definitely Related

There is evidence of exposure to the test drug, the temporal sequence of the AE onset relative to administration of the test drug is reasonable, and the AE is more likely explained by the test drug than by any other cause, and the AE shows a pattern consistent with previous knowledge of the test drug or test drug class.

12.2.3. Recording Adverse Events

All AEs and details for the events will be recorded in the subject's source document and eCRF. An AE should be documented in terms of a medical diagnosis and reported in standard medical terminology when possible. When this is not possible, the AE should be documented in terms of signs and/or symptoms observed or reported. It is important for the Investigator to only record 1 AE per line on the eCRF. Combination events (eg, nausea/vomiting), should be entered as 2 events.

The Investigator must determine the intensity of the AE as defined by:

- Mild: no medical interventions required, short lasting discomfort, and does not interfere with subject's daily activities
- Moderate: activity may be limited, and subject may require minimal medical therapy, intervention, or assistance
- Severe: definitely limits subject's daily activity that may require hospitalization and or intervention/therapy assess whether or not the study drug caused the AE

The Investigator will record whether the AE or AEs led to discontinuation of the subject from the study, record the outcome of the AE (unresolved, resolved, resolved with sequelae, death, or unknown), and determine if the AE is serious.

For this study, AEs and SAEs will be collected beginning with the start of dosing on Day 1 and will end 30 days after the last dose of study drug.

